5.5 Dosing Delays/Dose Modifications

During the dose escalation phase dose modifications of birinapant will only be permitted in Cycle 2 and beyond (section 5.5.1). During the first cycle, patients are assessed for DLTs and dose modifications may not be performed.

Following the completion of the first cycle of therapy and in the dose expansion phase, if an AE is assessed as related to study drug the dosing may be modified according to the starting cohort dose by reducing the dose of birinapant according to the schema in [Section 5.5.1](#) . In the case where causality cannot be assigned to only one of the agents, the Investigator should first dose de-escalate birinapant, followed by withholding pembrolizumab if required. There will be no pembrolizumab dose reductions permitted in this study (for pembrolizumab dosing rules, see Table 6)

Adverse events (both non-serious and serious) associated with pembrolizumab exposure may represent an immunologic etiology. These AEs may occur shortly after the first dose or several months after the last dose of treatment. Pembrolizumab must be withheld for drug-related toxicities and severe or life-threatening AEs as per [Section 5.5.2](#) and [Section 5.5.3](#) for supportive care guidelines, including use of corticosteroids. Dosing interruptions are permitted in the case of medical or surgical events or logistical reasons not related to study therapy (e.g., elective surgery, unrelated medical events, patient vacation, and/or holidays). Patients should be placed back on study therapy within 3 weeks of the scheduled interruption, unless otherwise discussed with the Sponsor. The reason for interruption should be documented in the patient's study record.

If a patient experiences an AE in cycle 2 or beyond in the dose escalation phase or in the dose expansion phase of the study, the Investigator may hold birinapant for up to 14 days. On resolution of the AE (or return to baseline) birinapant may be restarted at their prior dose, or de-escalated, depending on the type and severity of the event. After a delay of > 14 days, the Investigator should consider removing the patient from the study.

5.5.1 **Dose Modifications Schema and Supportive Care Guidelines for Birinapant**

The following dose modification schemas for **birinapant** are required for selected AEs below.

Cranial Nerve Palsy	Birinapant
≤ Grade 1	No change; initiate corticosteroids ^{1,2}
≥ Grade 2	Interrupt up to 14 days; may restart at same or one dose below initial dose received ²

¹Corticosteroids should be considered at the onset of any Grade cranial nerve palsy; the recommended dose is 1-2 mg/kg day of prednisone or prednisone-equivalent, until resolution or return to baseline.
² All patients that develop a cranial nerve palsy should have a blood sample taken to assess for HSV and VZV. Sites may also consider sending the patient for a MRI.

In the event of facial pain, ear pain, retro-orbital pain, or atypical or new-onset headache, it is recommended that birinapant be held, and that a course of nonsteroidal anti-inflammatory agents (NSAIDs), such as ibuprofen, be initiated, at an appropriate anti-inflammatory dose. If within 24 hours symptoms do not resolve, or worsen, or the patient develops a cranial neuropathy, a course of steroids (prednisone) should be initiated. Birinapant may be re-introduced at the resolution of the event, at the same dose or at a reduced dose (by 1 dose level) depending on the severity of the event, if the Investigator and the patient are in agreement.

Cytokine Release Syndrome	Birinapant
≤ Grade 1	Interrupt up to 14 days; initiate diphenhydramine, acetaminophen*. Restart at same dose.
Grade 2	Interrupt up to 14 days; initiate diphenhydramine, corticosteroids. Restart treatment at one dose level down
> Grade 2	Interrupt permanently; initiate diphenhydramine, corticosteroids.

*Diphenhydramine, acetaminophen or intravenous fluids should be considered at the onset of cytokine release syndrome, until resolution.

Management of Cytokine Release Syndrome (CRS): Cytokine release syndrome is defined in CTCAE v4.03 as a disorder characterized by nausea, headache, tachycardia, hypotension, rash, and shortness of breath. CRS occurs when lymphocytes (B cells, T cells, and/or natural killer cells) and/or myeloid cells (macrophages, dendritic cells, and monocytes) become activated and release inflammatory cytokines. In addition to the symptomatology defined under CTCAE, CRS may present with fever, chills, myalgias, and malaise.

Amylase or lipase Elevation	Birinapant
≤ Grade 1	No change
≥Grade 2	Interrupt up to 14 days; restart at same dose*.
*On second occurrence, after resolution or return to baseline, a dose reduction to one dose level down should be considered.	

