5.4 Dose-Limiting Toxicity and Recommended Phase 2 Dose

The inter-patient dose escalation of birinapant will be based on the number of patients that experience a DLT. A DLT is a clinically significant event attributed to birinapant, pembrolizumab, or the combination of the 2 study drugs, during the first cycle of drug therapy and is defined as follows:

Non-hematological toxicity:

- Common Toxicity Criteria for Adverse Event (CTCAE; 4.03) Grade 3 nausea, vomiting, or diarrhea despite maximal (according to treating investigator) anti-emetic or anti-diarrheal treatment and lasting > 48 hours; or Grade 4 vomiting or diarrhea;
- \geq Grade 3 other non-hematological toxicity, excluding isolated laboratory abnormalities without clinical sequelae, except for the following:
 - Prolonged (> 7 days) serum amylase or lipase elevation;
 - Prolonged (> 7 days) aspartate aminotransferase (AST) elevation;
 - Prolonged (> 7 days) alanine aminotransferase (ALT) elevation;All of which will be considered dose limiting.

Hematological toxicity:

- Grade 4 neutropenia;
- Grade \geq 3 neutropenia with fever > 38.3°C or > 38°C (> 100.9°F or > 100.4°F) for more than one hour;
- Grade \geq 3 thrombocytopenia with bleeding

Specific toxicity:

- Cytokine release syndrome (CRS); Grade 3 or 4. Furthermore, if a Grade >2 CRS occurs during the DLT period (Cycle 1), this also triggers the permanent discontinuation of all study dosing (birinapant AND pembrolizumab) with subsequent adequate care to treat the condition (see also sections 5.5.1 and 5.5.3).

If Day 8 of treatment is held due to toxicity then the event will be considered a DLT. A prolonged delay (> 2 weeks) in initiating Cycle 2 secondary to drug-related toxicity may be considered a DLT as judged by the SRC. Events related to disease progression, intercurrent illness, or concomitant medication will not constitute a DLT. Since patients are assessed for DLTs during the first cycle, dose modifications may not be performed. If a patient experiences a DLT that is deemed related to birinapant, the dose of birinapant may be restarted at a reduced level for Cycle 2 according to dose levels indicated in Table 2/[section 3](#) and the rules stated in [section 5.5](#), and the patient may remain on study.

The decisions to dose-escalate birinapant for each Dose Level are indicated in [Table 5](#) below.

Table 5 Escalation Decision Rules

Number of Patients with DLT at a Given Dose Level	Escalation-decision Rule

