8.1.2 Severity of an Adverse Event

Severity of AEs will be graded according to NCI CTCAE version 4.03.

AEs that are not included in the NCI CTCAE lists will be graded according to the NCI CTCAE general guideline for grades as follows:

- Grade 1** Mild, asymptomatic or mild symptoms; clinical or diagnostic observations only; intervention not indicated.
- Grade 2** Moderate, minimal, local intervention, or noninvasive intervention indicated; limiting age-appropriate instrumental activities of daily living (ADL), e.g., preparing meals, shopping for groceries or clothes, using the telephone, managing money.
- Grade 3** Severe or medically significant but not immediately life-threatening; hospitalization or prolongation of hospitalization indicated; disabling; limiting self-care ADL, e.g., bathing, dressing and undressing, feeding self, using the toilet, taking medications, and not bedridden.
- Grade 4** Life-threatening consequences; urgent intervention indicated.
- Grade 5** Death related to adverse event

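### Protocol Section 5.5.1 gives two birinapant instructions when facial pain or headache is followed by a cranial nerve palsy of Grade 1 or less

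*Protocol*

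**What the plan says.** Protocol Section 5.5.1 holds two texts on this toxicity.

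- **The table.** It belongs to a set of birinapant schemas that "are required for selected AEs below". For cranial nerve palsy of Grade 1 or less the entry is "No change; initiate corticosteroids". For Grade 2 or higher it is "Interrupt up to 14 days; may restart at same or one dose below initial dose received".
- **The paragraph after the table's footnotes.** It begins: "In the event of facial pain, ear pain, retro-orbital pain, or atypical or new-onset headache, it is recommended that birinapant be held". NSAIDs are started. If symptoms persist or worsen within 24 hours, "or the patient develops a cranial neuropathy, a course of steroids (prednisone) should be initiated". It then says: "Birinapant may be re-introduced at the resolution of the event, at the same dose or at a reduced dose (by 1 dose level", with the choice of dose depending on severity and the investigator and patient agreeing.

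Two other parts of the protocol bear on these texts.

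- **Section 5.5, general rule.** From Cycle 2 of escalation, and throughout expansion, the investigator may hold birinapant for up to 14 days after an adverse event. It may be restarted on resolution or return to baseline, at the prior dose or a lower one. Beyond 14 days, removal from the study should be considered. Dose modification is barred in Cycle 1 of escalation.
- **Section 5.4.** "If Day 8 of treatment is held due to toxicity then the event will be considered a DLT". Under Table 5, two or more DLTs among 3 to 6 patients stop escalation.

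**The concern.** The paragraph starts from pain or headache but does not stop there. It follows the patient into a cranial neuropathy, for which the table also has a row. It names no grade, makes no exception for Grade 1, and does not send the reader back to the table. A patient whose birinapant is held for facial pain, and who then shows a Grade 1 palsy, is dosed without change under one text and remains held under the other.

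The event matters to this trial. Cranial nerve palsy is a listed event of clinical interest (Section 8.4) and the stated reason for NSAID prophylaxis before each birinapant dose (Section 5.6). If sites resolve the conflict differently, patients with the same event will receive different exposure. The SAP's cumulative dose and relative dose intensity for birinapant (Section 5.5.6) would then combine two dosing policies. In Cycle 1 of escalation the choice also reaches the DLT count.

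**Working it through.** The plan states no figure on this point, so there is none to reproduce. The first step compares the two texts; the second and third size the consequence.

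**Step 1. The same patient under each text.** Take a patient with facial pain, birinapant held, followed by a cranial nerve palsy of Grade 1.

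| Question | Table | Paragraph |
|---|---|---|
| Force | Required | Recommended |
| Grade covered | 1 or less | None given |
| Next birinapant dose | Given, unchanged | Remains held |
| When dosing resumes | No interruption | At resolution |
| Dose on resuming | Unchanged | Same, or one level lower |
| Steroids | Started | Started |

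The rows on the next dose, resumption and dose level cannot all be satisfied together. Nothing in Sections 5.5 or 5.5.1 ranks the two texts. A palsy with no preceding pain or headache meets only the table, so no conflict arises there.

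**Step 2. Doses at stake within a 14-day hold.** Inputs: birinapant on Days 1 and 8 of a 21-day cycle (Section 5.3), and a hold of up to 14 days (Section 5.5).

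- Number the days from Day 1 of one cycle, so that doses fall on Days 1, 8, 22, 29 and so on.
- A 14-day hold starting on Day s covers Days s to s + 13.
- It catches both Day 22 and Day 29 when s is at most 22 and s + 13 is at least 29, that is, for s from 16 to 22. These are 7 of the 21 possible start days.
- On the other 14 start days it catches one dose.
- Average: (7 × 2 + 14 × 1) / 21 = 28 / 21 = 1.3 doses. The dosing rate gives the same: 2 × 14 / 21 = 1.3.

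For a full 14-day hold, the paragraph therefore withholds one or two doses that the table would give. A shorter hold can withhold fewer.

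**Step 3. Cycle 1 of escalation.** The general 14-day rule does not cover this cycle. Suppose the pain and the Grade 1 palsy both appear before Day 8. If the site follows the table, Day 8 is given and no DLT arises from a held dose. If it follows the paragraph and withholds Day 8 for toxicity, Section 5.4 makes the event a DLT. One patient counted differently can move a dose level from 0 to 1 DLT, or from 1 to 2, and 2 stops escalation under Table 5. Section 5.5 bars dose modification in this cycle, yet Section 5.4 expects that Day 8 may be held. The documents do not say whether the paragraph's hold is open to a site in Cycle 1.

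**The case against.** The best case against the point has four parts.

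1. **The texts differ in force.** The table is required, while the hold is recommended and re-introduction is permitted. A site could reasonably let the table govern once a palsy is diagnosed. That reading is open, but the protocol does not state it. On that reading, a site that keeps holding, as the paragraph recommends, departs from a required schema.
2. **The paragraph's trigger is pain or headache.** Its neuropathy clause calls only for steroids, which agrees with the table. The event that must resolve is not defined and could mean the pain alone. This stands as a possible reading. However, the clause does not lift the hold already in place, and nothing says that it ends when the table's row comes into play.
3. **The overlap may be rare.** It needs a painful presentation with a palsy still at Grade 1. The CTCAE grading of cranial nerve disorders is not reproduced in the documents. The general Grade 1 wording in Section 8.1.2, "Mild, asymptomatic or mild symptoms; clinical or diagnostic observations only; intervention not indicated", leaves room for mild symptoms but is given for events outside the CTCAE lists. The frequency is unknown. Nothing in Section 5.5.1 rules the combination out.
4. **Section 5.5 already bounds the hold.** This stands. A reader might infer that the paragraph allows an unlimited hold, and so conflicts with the table's 14 days at Grade 2 or higher. The documents do not support that: Section 5.5 applies resolution and the 14-day limit together from Cycle 2 of escalation and throughout expansion.

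**Conclusion.** The point holds for one group: patients whose facial, ear or retro-orbital pain or new or atypical headache is followed by a cranial nerve palsy of Grade 1 or less. For them Section 5.5.1 gives two birinapant instructions and does not say which governs. The size is one or two scheduled doses for a full 14-day hold, averaging 1.3 if the hold is equally likely to start on any day of the cycle. In Cycle 1 of escalation, the DLT status of the patient can also depend on the reading. The conclusion assumes that a palsy preceded by such symptoms can be Grade 1, which the documents neither confirm nor exclude.

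Three stronger inferences are not supported.

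- A larger dose difference would need a longer palsy. The documents give no palsy duration, and beyond 14 days Section 5.5 turns to considering removal.
- It may seem inconsistent that pain prompts a hold while a Grade 1 palsy without pain does not. Those are two separate rules and do not contradict each other; the choice between them is clinical.
- The Bell's palsy events that placed 63 mg/m² above the MTD (Section 1.6.1) were Grade 2, so they do not bear directly on the Grade 1 conflict. Nor does the SAP plan an estimate of palsy outcome under continued dosing; its dose-intensity summaries are descriptive.

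**What to change.** The sponsor should reconcile the table and the paragraph in Section 5.5.1. The revised text should state:

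- which instruction governs, by grade, once a cranial neuropathy follows pain or headache;
- which event must resolve before birinapant is re-introduced;
- how the instruction fits with the 14-day hold in Section 5.5 and with the Cycle 1 rules in Sections 5.4 and 5.5, including the counting of a held Day 8 dose as a DLT.

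No view is offered on which dosing instruction is right; that is for the sponsor to settle. The change is a few lines of wording at the next amendment and adds no visits, tests or patients.

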5.5.2 Dose Modification Schema for Pembrolizumab

Adverse events (both non-serious and serious) associated with pembrolizumab exposure may represent an immunologic etiology. These AEs may occur shortly after the first dose or several months after the last dose of treatment. Pembrolizumab must be withheld for drug-related toxicities and severe or life-threatening AEs. See [Section 5.5.3](#) for supportive care guidelines, including use of corticosteroids.

Dosing interruptions are permitted in the case of medical / surgical events or logistical reasons not related to study therapy (e.g., elective surgery, unrelated medical events, patient vacation, and/or holidays). Subjects should be placed back on study therapy within 3 weeks of the scheduled interruption, unless otherwise discussed with the Sponsor. The reason for interruption should be documented in the patient's study record.

5.5.3 Supportive Care Guidelines for Pembrolizumab

5.5.3.1 Dose Modification and Toxicity Management Guidelines for Pembrolizumab

Dose modification and toxicity management for immune-related AEs associated with pembrolizumab

AEs associated with pembrolizumab exposure may represent an immunologic etiology. These immune-related AEs (irAEs) may occur shortly after the first dose or several months after the last dose of pembrolizumab treatment and may affect more than one body system simultaneously. Therefore, early recognition and initiation of treatment is critical to reduce complications. Based on existing clinical trial data, most irAEs were reversible and could be managed with interruptions of pembrolizumab, administration of corticosteroids and/or other supportive care. For suspected irAEs, ensure adequate evaluation to confirm etiology or exclude other causes. Additional procedures or tests such as bronchoscopy, endoscopy, skin biopsy may be included as part of the evaluation. Based on the severity of irAEs, withhold or permanently discontinue pembrolizumab and administer corticosteroids. Dose modification and toxicity management guidelines for irAEs associated with pembrolizumab are provided in [Table 6](#).

Table 6 Dose modification and toxicity management guidelines for immune-related AEs associated with pembrolizumab

General instructions: Corticosteroid taper should be initiated upon AE improving to Grade 1 or less and continue to taper over at least 4 weeks. For situations where pembrolizumab has been withheld, pembrolizumab can be resumed after AE has been reduced to Grade 1 or 0 and corticosteroid has been tapered. Pembrolizumab should be permanently discontinued if AE does not resolve within 12 weeks of last dose or corticosteroids cannot be reduced to ≤ 10 mg prednisone or equivalent per day within 12 weeks. For severe and life-threatening irAEs, IV corticosteroid should be initiated first followed by oral steroid. Other immunosuppressive treatment should be initiated if irAEs cannot be controlled by corticosteroids.				
Immune-related AEs	Toxicity grade or conditions (CTCAEv4.0)	Action taken to pembrolizumab	irAE management with corticosteroid and/or other therapies	Monitor and follow-up
Pneumonitis	Grade 2	Withhold	Administer corticosteroids (initial dose of 1-2 mg/kg prednisone or equivalent) followed by taper	Monitor participants for signs and symptoms of pneumonitis Evaluate participants with suspected pneumonitis with radiographic imaging and initiate corticosteroid treatment Add prophylactic antibiotics for opportunistic infections
	Grade 3 or 4, or recurrent Grade 2	Permanently discontinue		
Diarrhea / Colitis	Grade 2 or 3	Withhold	Administer corticosteroids (initial dose of 1-2 mg/kg prednisone or equivalent) followed by taper	Monitor participants for signs and symptoms of enterocolitis (ie, diarrhea, abdominal pain, blood or mucus in stool with or without fever) and of bowel perforation (ie, peritoneal signs and ileus). Participants with \geq Grade 2 diarrhea suspecting colitis should consider GI consultation and performing endoscopy to rule out colitis. Participants with diarrhea/colitis should be advised to drink liberal quantities of clear fluids. If sufficient oral fluid intake is not feasible, fluid and electrolytes should be substituted via IV infusion.
	Grade 4	Permanently discontinue		

AST / ALT elevation or Increased bilirubin	Grade 2	Withhold	Administer corticosteroids (initial dose of 0.5- 1 mg/kg prednisone or equivalent) followed by taper	Monitor with liver function tests (consider weekly or more frequently until liver enzyme value returned to baseline or is stable
	Grade 3 or 4	Permanently discontinue	Administer corticosteroids (initial dose of 1-2 mg/kg prednisone or equivalent) followed by taper	
Type 1 diabetes mellitus (T1DM) or Hyperglycemia	Newly onset T1DM or Grade 3 or 4 hyperglycemia associated with evidence of β -cell failure	Withhold	Initiate insulin replacement therapy for participants with T1DM Administer anti-hyperglycemic in participants with hyperglycemia	Monitor participants for hyperglycemia or other signs and symptoms of diabetes.
Hypophysitis	Grade 2	Withhold	Administer corticosteroids and initiate hormonal replacements as clinically indicated.	Monitor for signs and symptoms of hypophysitis (including hypopituitarism and adrenal insufficiency)
	Grade 3 or 4	Withhold or permanently discontinue		
Hyperthyroidism	Grade 2	Continue	Treat with non-selective beta-blockers (e.g., propranolol) or thionamides as appropriate	Monitor for signs and symptoms of thyroid disorders.
	Grade 3 or 4	Withhold or permanently discontinue		
Hypothyroidism	Grade 2-4	Continue	Initiate thyroid replacement hormones (eg, levothyroxine or liothyronine) per standard of care	Monitor for signs and symptoms of thyroid disorders.
Nephritis and Renal dysfunction	Grade 2	Withhold	Administer corticosteroids (prednisone 1-2 mg/kg or equivalent) followed by taper.	Monitor changes of renal function
	Grade 3 or 4	Permanently discontinue		
Myocarditis	Grade 1 or 2	Withhold	Based on severity of AE administer corticosteroids	Ensure adequate evaluation to confirm etiology and/or exclude other causes

	Grade 3 or 4	Permanently discontinue		
All other immune-related AEs	Intolerable/persistent Grade 2	Withhold	Based on type and severity of AE administer corticosteroids	Ensure adequate evaluation to confirm etiology and/or exclude other causes
	Grade 3	Withhold or discontinue based on the type of event. Events that require discontinuation include and not limited to: Gullain-Barre Syndrome, encephalitis		
	Grade 4 or recurrent Grade 3	Permanently discontinue		

Withhold or permanently discontinue pembrolizumab is at the discretion of the investigator or treating physician. NOTE: For participants with Grade 3 or 4 immune-related endocrinopathy where withhold of pembrolizumab is required, pembrolizumab may be resumed when AE resolves to \leq Grade 2 and is controlled with hormonal replacement therapy or achieved metabolic control (in case of T1DM).
				

Dose modification and toxicity management of infusion-reactions related to pembrolizumab

Pembrolizumab may cause severe or life threatening infusion-reactions including severe hypersensitivity or anaphylaxis. Signs and symptoms usually develop during or shortly after drug infusion and generally resolve completely within 24 hours of completion of infusion. Dose modification and toxicity management guidelines on pembrolizumab associated infusion reaction are provided in Table 7.

Table 7 Pembrolizumab Infusion Reaction Dose modification and Treatment Guidelines

NCI CTCAE Grade	Treatment	Premedication at Subsequent Dosing

Grade 1
 
Mild reaction; infusion interruption not indicated; intervention not indicated
	
Increase monitoring of vital signs as medically indicated until the subject is deemed medically stable in the opinion of the investigator.
	
None


Grade 2
 
Requires therapy or infusion interruption but responds promptly to symptomatic treatment (e.g., antihistamines, NSAIDs, narcotics, IV fluids); prophylactic medications indicated for ≤24 hrs.
	
Stop Infusion. Additional appropriate medical therapy may include but is not limited to: IV fluids Antihistamines NSAIDs Acetaminophen Narcotics Increase monitoring of vital signs as medically indicated until the subject is deemed medically stable in the opinion of the investigator. If symptoms resolve within 1 hour of stopping drug infusion, the infusion may be restarted at 50% of the original infusion rate (e.g. from 100 mL/hr to 50 mL/hr). Otherwise dosing will be held until symptoms resolve and the subject should be premedicated for the next scheduled dose.
 
Subjects who develop Grade 2 toxicity despite adequate premedication should be permanently discontinued from further study drug treatment
	
Subject may be premedicated 1.5h (± 30 minutes) prior to infusion of pembrolizumab with: Diphenhydramine 50 mg po (or equivalent dose of antihistamine).
 
Acetaminophen 500-1000 mg po (or equivalent dose of analgesic).

Grades 3 or 4 Grade 3: Prolonged (i.e., not rapidly responsive to symptomatic medication and/or brief interruption of infusion); recurrence of symptoms following initial improvement; hospitalization indicated for other clinical sequelae (e.g., renal impairment, pulmonary infiltrates) Grade 4: Life-threatening; pressor or ventilatory support indicated
	
Stop Infusion. Additional appropriate medical therapy may include but is not limited to: Epinephrine** IV fluids Antihistamines NSAIDs Acetaminophen Narcotics Oxygen Pressors Corticosteroids Increase monitoring of vital signs as medically indicated until the subject is deemed medically stable in the opinion of the investigator. Hospitalization may be indicated. **In cases of anaphylaxis, epinephrine should be used immediately.
 
Subject is permanently discontinued from further study drug treatment.
	
No subsequent dosing

Appropriate resuscitation equipment should be available at the bedside and a physician readily available during the period of drug administration.
 
For further information, please refer to the Common Terminology Criteria for Adverse Events v4.03 (CTCAE) at http://ctep.cancer.gov
		

Other allowed dose interruption for pembrolizumab

Pembrolizumab may be interrupted for situations other than treatment-related AEs such as medical / surgical events or logistical reasons not related to study therapy. Subjects should be placed back on study therapy within 3 weeks of the scheduled interruption, unless otherwise discussed with the Sponsor. The reason for interruption should be documented in the patient's study record.

